6.3.5. Severity and duration of AECOPD

Total number of exacerbations recorded during the study, exacerbation rate (number of exacerbation per patient-year) and the proportion of COPD patients experiencing a certain number of exacerbations will be presented overall and per bacterial/viral species. The exacerbation rate per year will be reported with and without correction for early withdrawal (see Section 11.3).

Total number of exacerbations recorded during the study, the mean exacerbation rate per year and the proportion of COPD patients experiencing a certain number of exacerbations will be presented overall and divided by AECOPD severity.

The number and proportion of COPD patients experiencing a certain number of exacerbations will be presented overall and by GOLD grade at enrolment.

CONFIDENTIAL

201112 (EPI-NTHI-001 BOD APA)
 Statistical Analysis Plan Amendment 2 Final

The number of patients that report at least 1 AECOPD will be tabulated and descriptive statistics (N, mean, median, SD, minimum, maximum, first and third quartiles) on the average length of AECOPD episodes, as estimated by the investigator, will be presented, for any, mild, moderate and severe AECOPD.

Number of days between 2 consecutive exacerbations, as estimated by the investigator, will be summarized using the same descriptive statistics.

Descriptive statistics of the number of patients according to their percentage of days within an exacerbation period out of the total observation period as estimated by the investigator will be presented. For this analysis, the exacerbations for which the end date was unknown were not excluded and the length was estimated by the investigator as the average length per severity grade.

Results from the chest X-rays during exacerbation visit will be tabulated.

The percentage of scheduled visit in which the status of the patient is stable/recovered, or not recovered will be tabulated.

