3.1.1.1. Date of onset and end date of AECOPD

The date of onset is the first day (of at least 2 consecutive days) of worsening symptoms of COPD, as determined by the Investigator according to the Anthonisen criteria.

The end date should be based on when the investigator determines that the AECOPD symptoms have resolved. In determining this end date, consideration should be given to symptoms recorded in the electronic Diary Card and subject assessment during the phone calls.

Both start and end date of each confirmed AECOPD occurring from the screening visit to study conclusion will be recorded in the eCRF.

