9.2. Determination of sample size

The primary objective of this study is to describe the proportion of bacterial and viral pathogens (overall and by species) detected in sputum in stable COPD and during AECOPD.

Assuming around 90% of the All Enrolled Set participated in the study, on average 1 AECOPD visit and 80% of the above population set can provide an evaluable sputum sample at AECOPD, for 240, 200, 160, and 50 enrolled subjects, one may expect around 180, 140, 120, 40 sputum samples, respectively. Assuming that results from these sputum samples are independent and that the between country variability is much smaller than the within country variability, we would have the following 95% exact confidence interval for different incidences in sputum samples from exacerbations (see [Table 12](#)).

Table 12 Exact 95% confidence intervals of the percentage of occurrence of a specific bacterium from sputum collected during AECOPD

%	Number of evaluable sputum samples during AECOPD			
	N=180	N=140	N=120	N=40
5	[2.3 ; 9.3]	[2.0 ; 10.0]	[1.9 ; 10.6]	[0.6 ; 16.9]
10	[6.0 ; 15.3]	[5.6 ; 16.2]	[5.3 ; 16.8]	[2.8 ; 23.7]
20	[14.4 ; 26.6]	[13.7 ; 27.6]	[13.3 ; 28.3]	[9.1 ; 35.6]
30	[23.4 ; 37.3]	[22.6 ; 38.3]	[22.0 ; 39.0]	[16.6 ; 46.5]
40	[32.8 ; 47.6]	[31.8 ; 48.6]	[31.2 ; 49.3]	[24.9 ; 56.7]
50	[42.5 ; 57.5]	[41.4 ; 58.6]	[40.7 ; 59.3]	[33.8 ; 66.2]

N = total number of evaluable sputum samples during AECOPD.

One of the secondary objectives is to estimate the incidence rate of all-cause AECOPDs in the study population.

Assuming around 80% of the all enrolled set completed the study, for 240, 200, 160 and 50 subjects enrolled, one would have at least 190, 160, 130 and 40 subjects evaluable respectively. Assuming further that around 80% of the subjects can provide an evaluable sputum sample at AECOPD, this would lead to around 150, 130, 100, 30 subjects (see [Table 13](#)).

Table 13 95% confidence intervals of AECOPD incidence rates with different overdispersion values

			$\Phi = 1$		$\Phi = 1.5$		$\Phi = 2$	
0.2 AECOPD/ subject/ year			95% CI*		95% CI*		95% CI*	
T	n	Value (n/T)	LL	UL	LL	UL	LL	UL
30	6	0.20	0.04	0.36	0.00	0.40	-0.03	0.43
100	20	0.20	0.11	0.29	0.09	0.31	0.08	0.32
130	26	0.20	0.12	0.28	0.11	0.29	0.09	0.31
150	30	0.20	0.13	0.27	0.11	0.29	0.10	0.30
1 AECOPD/ subject/ year			95% CI*		95% CI*		95% CI*	
T	n	Value (n/T)	LL	UL	LL	UL	LL	UL
40	40	1.00	0.69	1.31	0.62	1.38	0.56	1.44
130	130	1.00	0.83	1.17	0.79	1.21	0.76	1.24

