160	160	1.00	0.85	1.15	0.81	1.19	0.78	1.22
190	190	1.00	0.86	1.14	0.83	1.17	0.80	1.20
2 AECOPD/ subject/ year			95% CI*		95% CI*		95% CI*	
T	n	Value (n/T)	LL	UL	LL	UL	LL	UL
40	80	2.00	1.56	2.44	1.46	2.54	1.38	2.62
130	260	2.00	1.76	2.24	1.70	2.30	1.66	2.34
160	320	2.00	1.78	2.22	1.73	2.27	1.69	2.31
190	380	2.00	1.80	2.20	1.75	2.25	1.72	2.28
3 AECOPD/ subject/ year			95% CI*		95% CI*		95% CI*	
T	n	Value (n/T)	LL	UL	LL	UL	LL	UL
40	120	3.00	2.46	3.54	2.34	3.66	2.24	3.76
130	390	3.00	2.70	3.30	2.64	3.36	2.58	3.42
160	480	3.00	2.73	3.27	2.67	3.33	2.62	3.38
190	570	3.00	2.75	3.25	2.70	3.30	2.65	3.35

* Normal approximation with variance = $\Phi n/T^2$, where Φ is the overdispersion factor for a Poisson distribution (calculations performed in Microsoft Excel).

T = Total number of evaluable subjects; n = Total number of exacerbations; CI = confidence interval; LL = lower limit; UL = upper limit.

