6.3.4. Incidence rates of AECOPD

This study will provide an estimate of average number of exacerbations per person per year, in a COPD population at increased risk of exacerbation (i.e. moderate to very severe COPD patients with a documented history of at least 1 moderate or severe AECOPD in the year prior to enrolment).

To compute the incidence rate all the exacerbations will be taken into account. The observation period is from visit 1 to visit 3 or from visit1 to the last visit performed for patients lost to follow up.

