6.3.5.2. Time to exacerbation

To investigate the effect of several baseline risk factors upon the time to first exacerbation since enrolment/first visit, Cox regression models will be fitted including several risk factors such as smoking status at enrolment (active smoker vs. former-smoker), number of exacerbation reported in the 12 months prior to enrolment (one, two and equal or above three), COPD grade at enrolment, age (40-49, 50-59, 60-69, ≥ 70 years), sex. Time to the first recurrence overall and by covariates will be depicted in Kaplan-Meier survival curves. Log-log survival curves will be displayed as well. If the proportionality of hazards assumption is met the log-log survival curves will be parallel for covariate strata. If there is an intersection between curves the covariate will be added as a stratification factor in the cox regression model.

To take into account that exacerbations may occur more than once over the follow-up time for a given patient, a Cox regression model for recurrent events using the counting process approach (Andersen, 1993) will be adopted (more details in section 6.3.5.2.1). The model will be fitted including smoking status at enrolment, history of exacerbation in the 12 months prior to enrolment, COPD severity at enrolment, age and sex as covariates.

Additional stratification/risk factor may be defined during the analyses.

CONFIDENTIAL

201112 (EPI-NTHI-001 BOD APA)
 Statistical Analysis Plan Amendment 2 Final

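### SAP 6.3.5 summarises days between consecutive AECOPD from completed gaps only, which understates the interval by an amount that depends on the exacerbation rate

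*SAP*

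**What the plan says.** SAP 6.3.5 states: "Number of days between 2 consecutive exacerbations, as estimated by the investigator, will be summarized using the same descriptive statistics". The statistics meant are those listed just before it for episode length: "N, mean, median, SD, minimum, maximum, first and third quartiles".

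The window is set in SAP 6.3.4: "The observation period is from visit 1 to visit 3 or from visit1 to the last visit performed for patients lost to follow up". Protocol Table 6 gives 182 days as the optimal length of each half (175 to 203 allowed), so 364 days nominally and 350 to 406 at the limits. Protocol 3.1.1.1 adds: "Both start and end date of each confirmed AECOPD occurring from the screening visit to study conclusion will be recorded in the eCRF". If gaps are counted from screening, which may be up to 42 days before Visit 1, the window reaches at most 448 days.

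Censoring is handled elsewhere, for other quantities. SAP 6.3.5.2 speaks of Kaplan-Meier curves for a first recurrence, but 6.3.5.2.1 defines the time variable as days to the first exacerbation, censored at last contact. That is the interval from enrolment to event one, not from event one to event two. The same section plans "a Cox regression model for recurrent events using the counting process approach", and 6.3.4.4 models the rate with log follow-up as offset. SAP 11.3 replaces no missing measurements; its one exception extrapolates yearly counts for withdrawals, not gaps.

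**The concern.** A gap has a value only when the second AECOPD occurs before Visit 3 or withdrawal. A patient with n AECOPD supplies n−1 completed gaps and leaves one open. A patient with exactly one supplies nothing, although that patient has been observed free of a second event for some time. No gap longer than follow-up can appear, and patients with many events contribute many short gaps.

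A mean or median labelled as days between consecutive exacerbations may well be taken as the usual time to the next one. At 1 AECOPD per year it would then sit beside an incidence rate, from the same report, that implies an interval more than three times as long.

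**Working it through.** **Inputs.** The documents give no figure for the gap. The rates come from protocol Table 13: "0.2 AECOPD/ subject/ year", "1 AECOPD/ subject/ year", "2 AECOPD/ subject/ year", and 3 per year. Table 13 also supplies the overdispersion factors, Φ = 1, 1.5 and 2. The window is W = 364 days.

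**Table 13 first.** The formula is n/T ± 1.96·√(Φn)/T. For T = 160, n = 160, Φ = 1 it gives 1.00 ± 1.96 × 12.65/160 = 1.00 ± 0.155, matching the printed 0.85 to 1.15. All sixteen rows reproduce to two decimals at the three values of Φ.

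**Mean completed gap.** Take a constant rate, ignore episode length, and let μ = rate × 364/365.25. Given n events in W, each completed onset-to-onset gap has mean W/(n+1), and there are n−1 of them. Pooling over patients:

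mean = W × Σₙ≥₂ pₙ(n−1)/(n+1) ÷ Σₙ≥₂ pₙ(n−1)

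For Poisson counts the two sums are A = 1 + e^(−μ) − 2(1 − e^(−μ))/μ and B = μ − 1 + e^(−μ). At 1 per year, μ = 0.99658, e^(−μ) = 0.36914, A = 0.10309 and B = 0.36572. The mean is 364 × 0.10309/0.36572 = 102.6 days. The true mean is 365.25/1 = 365 days, and 365.25/102.6 = 3.56.

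For Φ above 1, pₙ is negative binomial with variance/mean = Φ. The last two columns are for Φ = 1.

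| Rate/year | Completed-gap mean, Φ=1 | 365.25/rate | Ratio | Completed-gap mean, Φ=2 | Patients with ≥2 AECOPD | First gaps left open |
|---|---|---|---|---|---|---|
| 0.2 | 117 | 1826 | 6% | 92 | 1.7% | 90% |
| 1 | 103 | 365 | 28% | 83 | 26% | 58% |
| 2 | 87 | 183 | 48% | 73 | 59% | 31% |
| 3 | 74 | 122 | 61% | 64 | 80% | 16% |

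**Dependence on the rate.** A 15-fold change in rate moves the reported mean 117/74 = 1.6-fold. From 1 to 3 per year it moves 103/74 = 1.4-fold, while the true mean moves 3-fold.

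**Sensitivity.** At 1 per year and Φ = 1, windows of 350, 406 and 448 days give 99, 112 and 122 days. Assuming 14-day episodes and measuring from recovery to next onset, simulation gives 112, 100, 85 and 73 days at the four rates.

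**Medians and the remedy** (simulation, 400,000 patients per scenario, rates 1, 2 and 3 per year). At Φ = 1 the completed-gap medians are 85, 68 and 56 days, against true medians of 253, 127 and 84. Kaplan-Meier on the first gap per patient, censored at day 364, gives 254, 126 and 84; at 0.2 per year the median is not reached. With overdispersion the Kaplan-Meier medians are 218, 124 and 86 days (Φ = 1.5) and 196, 121 and 86 (Φ = 2), because patients with at least one AECOPD are then a higher-rate group.

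**The case against.** The best reply is that this is a peripheral item. The interval is not among the objectives or endpoints of either document, protocol 9.6 does not plan it, and SAP section 7 limits all analyses to supportive or hypothesis-generating use. Recurrence is already analysed with full follow-up through the negative binomial rate and the counting-process Cox model, and a reader can take 365.25/rate as an average interval. The number of open gaps can largely be recovered, since each patient with at least one AECOPD leaves one and 6.3.5 tabulates those patients. The SAP attaches no interpretation to the interval.

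Much of this stands and limits the importance of the point. It does not remove the bias. The Cox model gives covariate effects and the negative binomial model gives rates; neither produces or corrects the gap summary. A descriptive statistic should still describe what its label says.

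A reader might infer that the interval is grossly short whatever the rate, or nearly independent of it. The figures do not support that: at 3 per year the completed-gap mean is 61% of the true mean, and it falls 28% between 1 and 3 per year. The cohort is selected for prior exacerbation, and the counts include mild events and missed visits with records, so rates above 1 cannot be ruled out. Stronger overdispersion would shorten the completed gaps further, but goes beyond the plan's own range: a negative binomial with k = 1 at 2 per year implies Φ = 1 + 2/1 = 3, while Table 13 stops at 2.

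**Conclusion.** The point holds for this one descriptive table. Used as written, it understates the interval about 3.6-fold at 1 AECOPD per year, about 2-fold at 2 and by about 40% at 3, and it responds only weakly to the rate. The direction is the same for windows of 350 to 448 days and for Φ from 1 to 2.

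Three assumptions carry the size. The SAP does not say in words that only completed gaps count; that follows from plain statistics on pairs of events with no censoring rule. The hazard is taken as constant within patient, whereas SAP 6.4.4 itself distinguishes a high and a low season, and the documents give no gap distribution. With Φ above 1, 365.25/rate is a reference for the cohort average rather than the mean gap of any one patient.

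It would be wrong to infer that the primary proportions or the AECOPD incidence rates are biased by this; neither uses the gap. It is a worthwhile and inexpensive improvement, not a threat to the study's main results.

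**What to change.** In SAP 6.3.5, add a Kaplan-Meier estimate of time from the first AECOPD to onset of the second, using one gap per patient and censoring at last contact.

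- Report the probability of a further AECOPD by 30, 90 and 180 days, and the median if reached, with numbers at risk.
- Label it as applying to patients with at least one AECOPD.
- Measure from first onset to second onset. If recovery is preferred as the start, state how a missing or partial recovery date is handled; SAP 11.3.1 excludes such dates only when measuring episode length.
- Give any severity breakdown as probabilities only, where numbers allow.
- Do not pool all gaps in one Kaplan-Meier curve, because later gaps are subject to dependent censoring.
- Keep the raw-gap table only if labelled 'completed gaps only, patients with at least 2 AECOPD in the observation period', with the number of open gaps shown.

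The cost is one extra analysis on dates already collected. Its weakness is precision. At 1 per year about 58% of first gaps are censored. With Φ = 1 and 364 days of follow-up, the share of patients still at risk at the 254-day median is (1 − e^(−110/365.25)) × e^(−254/365.25) = 13%, or about 21 of the 160 evaluable subjects the protocol expects from 200 enrolled. The 30-, 90- and 180-day probabilities should therefore carry the message, with the median secondary.

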6.3.5.1. Seasonal distribution

Seasonal distribution of the exacerbations (total number of exacerbations, AECOPD events and of AECOPD events containing NTHi, Mcat, Strep, Enterovirus/HRV, QPCR-Rhino and Influenza A and B) regardless of intensity will be reported by month.

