4.1. Number of subjects/ centres

The target is to enrol approximately 200 eligible moderate to very severe COPD patients. Refer to Section 9.2 for a detailed description of the criteria used to estimate the sample size.

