^j Only if clinically indicated to exclude another cause of worsening of symptoms (e.g. pneumonia). If a chest X-ray is clinically indicated but a chest X-ray/ CT scan has already been taken for that AECOPD as part of medical care before the study AECOPD visit takes places, the results of that chest X-ray/ CT scan can be used. All cases of pneumonia (including all signs and symptoms assessed to confirm pneumonia) should be documented in the eCRF.

^k Sputum can be collected spontaneously or can be induced, as per investigator judgement. Sputum sampling should only be done if, in the opinion of the investigator, it is safe for the subject.

^l Physical examination should be done only if necessary by the investigator or delegate.

^m AECOPD severity grading as indicated in Table 2.

ⁿ Non-serious AEs will be recorded in the eCRF and will not be entered into the safety database.

^{*} Refer to Table 10 for description of which AE/SAEs are collected in this study.

Table 6 presents the intervals between study visits.

Table 6 Intervals between study visits

Interval	Optimal length of interval	Allowed interval ¹
Screening Visit (pre-Month 0) → Visit 1	± 14 days	≤42 days before Visit 1
	Scheduled study visits	
Visit 1 (Month 0) → Visit 2 (Month 6)	182 days	175 - 203 days
Visit 2 (Month 6) → Visit 3 (Month 12)	182 days	175 - 203 days
AECOPD-driven study visit(s) and/ or phone contacts		
Onset AECOPD symptoms → AECOPD Visit	-	max 96 hours ²

¹ If an AECOPD occurs at the time one of the scheduled study visits is planned, the stable study visit should be rescheduled to a later date, when the subject is stable again and within the time window specified. In consultation with GSK, the concluding visit (Visit 3, Month 12) may however exceptionally be conducted outside of the allowed interval if necessary by the investigator.

² AECOPD visits will be scheduled as soon as possible after the onset of AECOPD symptoms as recorded in the electronic Diary Card or confirmed by the subject (maximum 96 hours after and, if applicable, preferably before starting treatment with antibiotics).

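### Seasonal AECOPD results are event counts by month without patient-time at risk, so uneven enrolment combined with withdrawal or follow-up other than 12 months can look like a mild season

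*SAP*

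**What the plan says.** SAP 6.3.5.1 (Amendment 2) describes the output as "total number of exacerbations, AECOPD events and of AECOPD events containing NTHi" and further named pathogens, and these "regardless of intensity will be reported by month". It mentions no denominator, number under observation or rate. It does not say whether the same calendar month is pooled over years, or from which date events count.

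Patient-time appears only in whole-study analyses. SAP 6.3.4.4 uses log follow-up as an offset. SAP 6.3.5 and 11.3 give an annual rate with and without a correction for early withdrawal. Season in SAP 6.4.4 is a two-level covariate in a within-patient conditional logistic model, which yields no monthly incidence.

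On exposure, SAP 6.3.4 defines the incidence period: "The observation period is from visit 1 to visit 3 or from visit1 to the last visit performed for patients lost to follow up". Protocol 3.1.1.1 starts recording earlier, because episodes "occurring from the screening visit to study conclusion will be recorded in the eCRF", and Table 6 in Protocol 6.3 allows screening "≤42 days before Visit 1". The same table sets each of the two inter-visit intervals at 182 days, with 175 to 203 allowed. Protocol 9.2 plans on incomplete follow-up: "Assuming around 80% of the all enrolled set completed the study".

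**The concern.** A count of events in a month is the event rate multiplied by the number of patients under observation. If that number varies over the calendar, the counts vary even when the rate is constant. Three features of the plan allow it to vary: patients who leave early miss the later part of their year, completers may be followed for less or more than 12 months, and episodes are recorded during screening.

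An exposure gradient is smooth, so it moves adjacent months in the same direction and does so in every series, overall and per pathogen. That is the shape a reader looks for in a seasonal display. The SAP allows for unequal follow-up in its annual rate (6.3.5), but in the subsection that follows, where exposure varies by calendar month as well, it does not.

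**Working it through.** **The plan's own exposure figures.** At 80% completion, 200 × 0.80 = 160, as stated in Protocol 9.2. Table 13 at "1 AECOPD/ subject/ year", T = 160 and Φ = 1 gives 1 ± 1.96 × √160 / 160 = 0.85 to 1.15, as printed. The seasonal section states no figure to reproduce.

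**Inputs.** 200 patients (Protocol 4.1: "The target is to enrol approximately 200 eligible moderate to very severe COPD patients"). Follow-up of 2 × 182 = 364 days nominal, or 2 × 175 = 350 to 2 × 203 = 406 days allowed (Table 6). Withdrawal of 20% (Protocol 9.2). The event rate is held constant, so any monthly pattern is artefact. My assumptions, because the documents do not give them: entry uniform over a window, and withdrawal uniform over follow-up.

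**Formula.** The probability of still being observed t days after Visit 1 is S(t) = 1 − w·t/F for t < F, where w is the withdrawal fraction and F the planned follow-up. Exposure in a calendar month is the sum of S over all patients and all days falling in that month, pooled over years.

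**A case to check by hand.** All patients enter on one day, F = 365 and w = 0.20. The first month averages 1 − 0.20 × (1/24) = 0.992 and the last 1 − 0.20 × (23/24) = 0.808. The ratio is 1.23. With w = 0 it is 1.00, because every patient covers every month once.

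**Excess of the highest over the lowest pooled month:**

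| Enrolment period (months) | 2 | 4 | 6 | 9 | 12 |
|---|---|---|---|---|---|
| 364 days, 20% withdraw | 18% | 14% | 10% | 5% | 0% |
| 364 days, 10% withdraw | 8% | 7% | 5% | 2% | 0% |
| Completers spread evenly over 350–406 days, 20% withdraw | 35% | 23% | 16% | 9% | 0% |

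At 364 days with no withdrawal the excess is at most 2% for any of these windows. Follow-up length alone can matter: with 91-day entry and no withdrawal, the ratio is 1.20 if everyone is followed for 350 days and 1.45 if everyone is followed for 406. Those are extremes.

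**Scale against noise.** Expected follow-up is 200 × (364/365) × (1 − 0.20/2) ≈ 180 patient-years. At 1 AECOPD per year that is 180 events, or 15 per month, with Poisson SD √15 ≈ 4. With 91-day entry starting in October, 364 days and 20% withdrawal, expected counts run from 13.7 (September) to 16.4 (January), a range smaller than one SD.

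**Adjacent months together.** With 91-day entry, 364 days and 20% withdrawal, the October–March to April–September count ratio lies between 0.92 and 1.08, depending on the start month. With about 90 events in each half-year, the standard error of the log ratio is √(1/90 + 1/90) ≈ 0.15, against log 1.08 ≈ 0.08. At 3 AECOPD per year, the highest rate in Table 13, there are about 270 events per half and the standard error is √(2/270) ≈ 0.09, so artefact and noise are then of similar size.

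**Chronological display.** With entry over 365 days, 364-day follow-up and 20% withdrawal, the number under observation rises from about 8 to 174 and falls back to about 1. Enrolment then determines the shape.

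**After the fix.** Dividing each month's events by that month's patient-time returns the constant rate, with a max/min ratio of 1.00 in every scenario.

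**The case against.** The strongest reply is that the effect is small and the output modest. With months pooled and a full 12 months per patient, entry dates cancel. Enrolment spread evenly over a year leaves no pattern at all. At about 15 events a month, chance alone gives a typical max/min ratio of roughly 2.3 to 2.4, well above any figure in the table. The 20% may also be too high here: it refers to the All Enrolled Set, whereas the FAS (SAP 5.3) excludes patients who discontinue at Visit 1. The protocol sets no seasonal objective, SAP section 7 treats all analyses as descriptive, and the mock tables are a separate document, so a denominator there cannot be excluded. For pathogens, total AECOPD events appear beside positive ones, so a monthly share can be formed in which patient-time cancels.

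Most of this stands as a limit on importance. It does not remove the gap. An exposure gradient is systematic, does not average out as counts grow, and can be removed with dates already held. The pathogen share is only partly protected, because some AECOPD events have no evaluable sputum (Protocol 9.2 assumes 80% provide one), so the share can move with sampling. The SAP text should carry the rule whatever the mock tables show.

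**Conclusion.** The point holds, as a minor one. SAP 6.3.5.1 plans monthly counts without patient-time, and nothing else in the documents supplies it for this output. With months pooled and 20% uniform withdrawal, the false excess of the highest over the lowest month ranges from 0% to about 18% at nominal follow-up, and to about 35% if completers are spread over the whole allowed window, as enrolment shortens from 12 months to 2. These sizes rest on assumed enrolment, withdrawal and follow-up patterns, since no enrolment calendar is given.

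Three stronger readings are not supported. A reader might infer that enrolment timing alone creates a false season; in pooled months with 12-month follow-up it does not, and uneven entry must combine with withdrawal or off-nominal follow-up. A reader might take the larger percentages as the expected size; they require completers across the full 350 to 406 days, although Table 6 gives 182 days per interval as optimal. A reader might extend the point to the overall incidence rates; those use a follow-up offset and are unaffected.

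**What to change.** In SAP 6.3.5.1:

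- State whether calendar months are pooled over years or shown chronologically.
- Count only events with onset between Visit 1 and end of follow-up, matching the observation period in 6.3.4. Without this, episodes recorded during the screening interval of up to 42 days would enter the numerator with no matching time at risk.
- Beside each count, report patient-months at risk and the AECOPD rate per patient-month.
- For the pathogen series, also show the number of AECOPD events with an evaluable sputum sample in that month, so that a change in sampling is not read as season.

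The cost is some programming to split each patient's follow-up by calendar month from visit and onset dates already collected. No new data are needed and no other planned analysis changes.
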